2.3 Study Design

PVO-1A-202 Part B is a Phase 2, multicenter, event-based, open-label extension of Study PVO-1A-201. This open-label extension will give subjects who completed Study PVO-1A-201 (including any subject who participated in Part A of Study PVO-1A-202) the opportunity to be followed for up to 2 years.

Subjects in the Adult Cohort will follow all procedures and undergo all assessments as specified in the Schedule of Assessments in Table 1 of the protocol. Site visits will occur at Part B Screening and at Study Months 12 and 24. The visit window for the visits at Study Months 12 and 24 is +/- 2 months where Study Day 1 is the date of screening in Part B. Remote visits (assessments performed at home or at a local medical facility) and telephone contact with the study site will occur every 3 months unless the Investigator deems that a site visit is necessary. The visit window for remote visits is +/- 2 weeks. Urine pregnancy tests will be performed each month for female subjects of childbearing potential.

Subjects in the Adult and Pediatric Cohorts receiving flare-up based treatment will follow all procedures and undergo all assessments as specified in the Schedule of Assessments in Table 2 of the protocol. These subjects will have site visits at Flare-Up Screening/Baseline (as soon as possible after the start of the flare-up) and at Flare-Up Day 84/end-of-treatment (EOT); and remote visits, where possible, at Flare-Up Days 14, 28, 42, 56, and 70. Should treatment be extended beyond Flare-up Day 84, 10 mg palovarotene (or the dose-equivalent) will be administered, in 4-week increments, until the flare-up resolves, with remote visits performed every 2 weeks while on treatment. The visit window is +/- 3 days where Flare-Up Day 1 is the date of first dose of flare-up based palovarotene except for Flare-up Day 84/EOT where the visit window is -3 days. Note that for analysis, visits will be displayed as Flare-Up Day 1, Flare-Up Week 2, Flare-Up Week 4, Flare-Up Week 6, Flare-Up Week 8, Flare-Up Week 10, Flare-Up Week 12, Flare-Up Week ## (for extended treatment), and EOT.

Pharmacokinetic blood samples will be collected within the first 7 days of starting flare-up based treatment and at Flare-up Day 84 at 0, 3, 6, 10, and 24 hours post-dose for the first treated flare-up only.

To assess an adequate number of flare-ups with the new dosing regimens, it is anticipated that each subject will participate in Part B of the study for approximately 18-24 months. Once a flare-up has resolved, the Adult Cohort subjects will resume non-flare-up based treatment of 5 mg once daily. Initiation of flare-up based treatment for a new flare-up can occur at any time after resolution of the prior flare-up.

Data regarding the original flare-up for those subjects from Study PVO-1A-201 will be collected at the Part B Screening visit (when the subject signs the informed consent) for the Adult Cohort according to the Schedule of Assessments in Table 1 of the Protocol; or at the Study Month 12 visit (starting from initial enrollment into Study PVO-1A-202) for the Pediatric Cohort according to the Schedule of Assessments in Table 3 of the Protocol.

Assessments for the Study Month 12 visit can be performed in conjunction with any of the site visits associated with flare-up based treatment (Flare-up Screening or Flare-up Day 84) as long

as those visits are within 5 months before or after the scheduled Study Month 12 visit. Subjects on Non-Flare-up dosing regimen will also be contacted by telephone at Study Months 6, 18, and 24 to assess concomitant medications and adverse events (AEs). The visit window is +/- 2 weeks where Day 1 is the date of informed consent for Part A.

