4.5 Pharmacokinetic Population

The Pharmacokinetic (PK) Population will include all subjects in the Flare-up Population who have sufficient blood samples collected for valid estimation of PK parameters. The analysis will be stratified as before for the Flare-up Population.

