7.9 Columbia-Suicide Severity Rating Scale

Suicidal ideation and behavior will be assessed using the Columbia-Suicide Severity Rating Scale (C-SSRS).

Data listings will be provided for (1) all C-SSRS results; and (2) for subjects reporting any type 4 or type 5 suicidal ideations.

8 Pharmacokinetics Data

Pharmacokinetics will be assessed within 7 days of flare-up based treatment initiation and at the end of treatment for the first treated flare-up. Blood samples will be taken at 0, 3, 6, 10, and 24 hours post-dose.

Plasma palovarotene concentrations will be summarized with descriptive statistics (number of non-missing values, arithmetic mean, standard deviation, standard error, coefficient of variation, geometric mean, median, minimum, and maximum). All plasma concentrations below the limit of quantification (LOQ) will be set to zero for the purpose of calculating descriptive statistics. If

at any time point, 1/3 or more of subjects have <LOQ values, descriptive statistics will not be calculated at that time point. PK concentrations will be imputed using the following:

- If 0-hour concentration missing, then 24-hour concentration used to replace the missing concentration.
- If 24-hour concentration missing, then 0-hour concentration used to replace the missing concentration.
- Invalid 24-hour concentrations were replaced with the 0-hour concentrations. Twenty-four-hour concentrations were determined to be invalid if concentration is greater than the 10-hour value (i.e. assumed to have been obtained after next day dose instead of before next day dose).

If any other blood sample collections are missing, PK parameters will not be assessed. Actual sampling times will be used for the PK analysis, if available. Nominal sampling times will be used for descriptive statistics.

Individual concentration-time profiles for palovarotene will be presented (linear and semi-logarithmic scales). Arithmetic means (+/- standard deviation) concentration-time profiles will also be presented (linear and semi-logarithmic scales).

An exploration of the effects of body weight on PK will be performed as the data allow.

The PK analysis of palovarotene will be conducted using model-independent methods as implemented in WinNonlin™. The PK variables analyzed will include $AUC_{0-24(ss)}$, $C_{max(ss)}$, $C_{min(ss)}$, $T_{max(ss)}$, CL/F , λ_z , and $t_{1/2z}$ at steady-state. The PK variables are defined as follows:

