$AUC_{0-24(ss)}$	Area under the concentration versus time curve over the 24-hour dosing interval; calculated using linear trapezoid rule.
$C_{max(ss)}$	Maximum or peak measured plasma concentration at steady-state.
$C_{min(ss)}$	Minimum or trough measured plasma concentration at steady-state.
$T_{max(ss)}$	Time of maximum or peak measured plasma concentration at steady-state, obtained by inspection.
CL/F	Clearance defined as: $Dose/AUC_{0-24(ss)}$.
λ_z	Terminal rate constant
$t_{1/2z}$	Apparent terminal elimination half-life; calculated as $\ln(2)/\lambda_z$. The number of data points included in the regression will be determined by visual inspection, but a minimum of three data points in the terminal phase, excluding C_{max} , will be required to estimate λ_z .

9 Changes from Protocol

For the purposes of clarity and consistency of nomenclature, the Flare-up Rate Population described in the protocol was renamed as the Non-Flare Treated Population.

The initial secondary objective listed in Section 2.1.2 was not included in Amendment 3 of the protocol for Study PVO-1A-202 Part B or Amendment 1 of the protocol for Study PVO-1A-204.

The protocol describes the primary comparison of outcomes to be from data collected from the NHS and Phase 2 study. These comparisons will be performed in a future analysis and the analysis described here will instead focus on comparisons solely from Study PVO-1A-202 Part B between treatment groups of PVO 20/10 mg and Prior Non-Flare-up/PVO 20/10 mg, for flare based analyses; and treatment groups of treated, untreated, or no-flares, for WBCT based analyses.

10 References

3. D'Agostino, RB., Jr., Tutorial in Biostatistics: Propensity Score Methods for Bias Reduction in the Comparison of a Treatment to a Non-Randomized Control Group. *Statistics in Medicine*, 1998, 17, 2265-2281.

Appendices

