
(weight-adjusted doses for skeletally immature subjects). Additional knee and hand/wrist radiograph assessments will also be performed every 3 months (± 2 weeks) in skeletally immature subjects who (1) received flare up dosing in the period of time since their last assessment; and (2) had not achieved 100% skeletally maturity on their last assessment.

Off Treatment Part D:

No study drug will be administered in Part D. For skeletally immature subjects in Part D, added Year 1 (Y1) and Year 2 (Y2), post last dose of study treatment assessments that include linear height, knee height, physical exam, vital signs, radiographic assessments of the knee and hand/wrist, low-dose WBCT imaging, adverse events, and concomitant medications. Once subjects reach skeletal maturity their participation in Part D will end. The total duration of participation in Part C and Part D combined is a maximum of 4 years (± 1 month).

Pharmacokinetics

The pharmacokinetics (PK) of palovarotene dosing will be assessed at the first 3-month safety assessment during non-flare-up based treatment; if samples cannot be or were not obtained during the first 3-month safety assessment, or if subjects are on flare-up based treatment, then PK blood samples for non-flare-up treatment can be obtained during any subsequent 3-month safety visit.

Pharmacokinetics (PK) will also be assessed twice during flare-up based treatment: once during the 20-mg regimen at any time between Study Days 4 to 28, and once during the 10-mg regimen at any time between Study Days 32 to 84, for the first treated flare-up only. If this is not possible for the first treated flare-up, PK blood samples can be obtained during any subsequent flare-up dosing cycle. Pharmacokinetic blood samples will be collected at pre-dose and 3, 6, 10, and 24 hours post-dose. Subjects who underwent PK assessment under PVO-1A-202 Protocol Amendment 3 (Part B) will not have PK assessed again; however, these subjects will require a non-flare-up treatment PK assessed at a 3-month safety visit.

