If the subject experiences intolerable side effects, the dose may be reduced to the next lower dose; if the subject is already receiving the lowest possible dose as shown in the Table 1, then study drug will be discontinued. Treatment may be extended after the 84-day treatment period (flare-up based dosing) if the flare-up is ongoing and continue until the flare-up resolves. Dosing will be extended in 4-week intervals based on clinical signs and symptoms as assessed by the Investigator, with remote visits performed every 4 weeks while on treatment. In the event the subject requires dose de-escalation due to an intolerable side effect for a previous flare-up, then the dose the subject will receive for a subsequent flare-up will be determined by the Investigator and the Medical Monitor.

Should a subject experience an intercurrent flare-up (defined as a new flare-up or marked worsening of the original flare-up), or if the Investigator confirms the presence of a substantial high-risk traumatic event likely to lead to a flare-up, at any time during flare-up based treatment, the 12-week dosing regimen will restart upon new intercurrent flare-up confirmation by the Investigator (ie, 4 weeks of 20 mg palovarotene followed by 8 weeks of 10 mg palovarotene [or weight-based equivalent]). A Flare-up Cycle will include the first flare-up or traumatic event and any subsequent intercurrent flare-ups or traumatic event during the same dosing period. Flare-Up Cycle Safety Day 1 is defined as the first day that study drug is administered for the first flare-up or traumatic event during that cycle. Safety assessments will be performed on Flare-up Cycle Safety Day 1, at 4 weeks, and every 8 weeks thereafter until treatment of the last flare-up or traumatic event in the Flare-up Cycle is completed. If any flare-up in a cycle has not resolved after 12 weeks, treatment and safety assessments will be extended and 10 mg palovarotene (or the weight-based equivalent) will be administered in 4-week intervals until all the flare-ups resolve and flare-up based treatment has been completed. It is possible that subjects may experience more than one Flare-up Cycle during the study.

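### Part B allows the first (20-mg) PK profile before steady state, yet reports all its parameters as steady-state and substitutes 0-h and 24-h values without condition

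*SAP*

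**What the plan says.** **Part B sampling.** Section 2.3 reads: "Pharmacokinetic blood samples will be collected within the first 7 days of starting flare-up based treatment", with a second set at Flare-up Day 84. Section 8 repeats this: "Pharmacokinetics will be assessed within 7 days of flare-up based treatment initiation and at the end of treatment for the first treated flare-up". Samples are at 0, 3, 6, 10 and 24 h. Section 2.4 gives 20 mg for 28 days and then 10 mg for 56 days, so the first profile belongs to the 20-mg step and the Day 84 profile to the 10-mg step.

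**Part B analysis.** Section 8 lists all PK variables as steady-state quantities. The peak, for example, is defined as "Maximum or peak measured plasma concentration at steady-state". AUC uses the linear trapezoid rule over 24 h, and CL/F is dose divided by that AUC. A missing 0-h value is filled from 24 h. In the other direction: "If 24-hour concentration missing, then 0-hour concentration used to replace the missing concentration". A 24-h value above the 10-h value is called invalid and is also replaced by the 0-h value. None of these rules depends on the day of sampling.

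**Part B strata.** On the PK Population, Section 4.5 says: "The analysis will be stratified as before for the Flare-up Population". Section 4.3 splits that population by whether non-flare-up treatment preceded the flare-up regimen.

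**Part C.** Sections 2.2 and 8 keep the substitutions but sample the 20-mg regimen only from Day 4, and the other step "once during the 10-mg regimen at any time between Study Days 32 to 84, for the first treated flare-up only". Section 2.3 adds that, after an intercurrent flare-up, "the 12-week dosing regimen will restart upon new intercurrent flare-up confirmation by the Investigator".

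**The concern.** Replacing a 24-h value by a 0-h value, or the reverse, is sound only when the pre-dose concentration equals the concentration at the end of the dosing interval, which is what steady state means. On Flare-up Day 1 the pre-dose value is zero in a subject with no drug on board, or a 5-mg trough in a subject on chronic dosing, while the 24-h value follows a 20-mg dose. The same mismatch makes the steady-state label wrong for AUC, Cmin and CL/F even with no sample missing.

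PK during the first treated flare-up is a secondary objective of Part B (Section 2.1.2). The planned strata divide subjects by exactly the factor that sets the Day 1 starting concentration. A table by stratum could therefore show a difference that reflects only time on drug.

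**Working it through.** **Stated figure.** The documents give no half-life, accumulation ratio, AUC or clearance, so there is nothing to reproduce.

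**Inputs from the SAP.** Sampling at 0, 3, 6, 10 and 24 h; linear trapezoid; CL/F = Dose/AUC; 20 mg on Days 1–28 and 10 mg on Days 29–84; prior stratum on 5 mg daily.

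**Assumptions, not from the SAP.** One compartment, linear kinetics, absorption rate 0.7/h, prior stratum at steady state on 5 mg, half-life varied from 4 to 36 h. An absorption rate of 0.5/h moves the Day 1 AUC fractions below by about 0.01 at most.

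**Results that need no half-life (Day 1 profile).**
- Without prior drug, the 0-h value is zero, so Cmin(ss) is zero.
- With prior 5 mg and dose-proportional kinetics, the 0-h value is 5/20 = 0.25 of the 20-mg steady-state trough.
- If 24 h is filled from a zero 0-h value, at most the 6-h and 10-h points remain usable on a log scale after Cmax. Section 8 requires three terminal points for the rate constant.

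**Approximate formula.** With very fast absorption and ke = ln 2 / half-life, Day 1 AUC over steady-state AUC is 1 − exp(−24ke) without prior drug. Prior 5 mg adds 0.25·exp(−24ke). At 12 h, exp(−24ke) = 0.25, giving 0.75 and 0.75 + 0.0625 = 0.8125.

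**Five-point trapezoid, Day 1, relative to the same trapezoid at 20-mg steady state (no prior drug / prior 5 mg).**

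| Half-life | AUC fraction | CL/F ratio | AUC, 24 h filled from 0 h | AUC, 0 h filled from 24 h |
|---|---|---|---|---|
| 4 h | 0.978 / 0.983 | 1.02 / 1.02 | 0.953 / 0.964 | 0.983 / 0.987 |
| 6 h | 0.921 / 0.941 | 1.09 / 1.06 | 0.861 / 0.896 | 0.934 / 0.950 |
| 12 h | 0.719 / 0.790 | 1.39 / 1.27 | 0.609 / 0.707 | 0.743 / 0.807 |
| 24 h | 0.471 / 0.603 | 2.12 / 1.66 | 0.365 / 0.523 | 0.494 / 0.620 |

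If both strata were sampled on Day 1, the spurious AUC ratio between them would be 0.941/0.921 = 1.02 at 6 h, 0.790/0.719 = 1.10 at 12 h and 0.603/0.471 = 1.28 at 24 h.

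**Later days, AUC fraction (no prior drug / prior 5 mg).**

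| Half-life | Day 2 | Day 3 | Day 4 | Day 7 |
|---|---|---|---|---|
| 12 h | 0.930 / 0.947 | 0.982 / 0.987 | 0.996 / 0.997 | 1.000 / 1.000 |
| 24 h | 0.735 / 0.802 | 0.868 / 0.901 | 0.934 / 0.950 | 0.992 / 0.994 |
| 36 h | 0.588 / 0.691 | 0.740 / 0.805 | 0.836 / 0.877 | 0.959 / 0.969 |

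**Day 84.** This is day 84 − 28 = 56 of the 10-mg step. The fraction is 1.000 at half-lives of 9, 24 and 36 h.

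**Part C step-down.** A restart of 20 mg on cycle Day 30 runs through Day 57, so the first day back on 10 mg is Day 58, inside the 32-to-84 window. The pre-dose value is then a 20-mg trough, twice the 10-mg one. The approximate ratio is 1 + exp(−24ke): 1.06, 1.25 and 1.50 at 6, 12 and 24 h. The five-point trapezoid gives 1.08, 1.28 and 1.53. Here AUC is too high and CL/F too low.

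**The case against.** - **Day 1 is allowed, not prescribed.** A reader might infer that Part B samples on the first day of dosing. The text does not say so. It gives a seven-day window, and nothing shows how many profiles fall on Days 1 to 3. The protocol schedule, which is not shown, may be narrower. This stands, and it limits the claim to what the SAP permits. Early sampling is still plausible: the only scheduled visit in that week is Flare-up Screening/Baseline, and the next is Day 14.
- **Half of the profiles are sound.** A reader might infer that Part B exposure is understated overall. The Day 84 profile is at steady state, so only the first profile is open to the error.
- **The substitution does not act in one direction.** Filling 0 h from 24 h raises a Day 1 AUC slightly; only the reverse lowers it. Both apply only to missing or invalid samples. This stands.
- **Part C as a breached standard.** The Part B SAP rests on Amendment 3 (March 2016) and the Part C SAP on Amendment 4 (September 2017) and later. The later windows are a useful model, not a rule that Part B broke.
- **Part C as the same bias.** A reader might expect the same direction there. A step from 20 to 10 mg reverses it. It is also unclear how often it applies: sampling is tied to the first treated flare-up, with later cycles only as a fallback.
- **Limited consequence.** PK is summarised descriptively and no test between strata is planned. Section 4.5 also requires enough samples for valid estimation, but a complete Day 1 profile meets that requirement, so it does not screen out the error.

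**Conclusion.** The point holds as a fault in the analysis rule: Part B can label and impute a profile as steady-state with no check that it is. For a Day 1 profile the direction is certain for Cmin, AUC and CL/F when no sample is substituted, and the error is larger without prior 5 mg. The size is not known, because it depends on an unstated half-life and on the actual sampling days. Under the assumed model the Day 1 AUC shortfall without prior drug runs from about 2% at a 4-h half-life to 53% at 24 h. By Day 4 it is under 1% up to 12 h, but 7% at 24 h and 16% at 36 h. The documents do not support a claim that Part B exposure is understated in general, or that the strata will differ by a given amount. The Part C issue is real but of opposite sign, and depends on an intercurrent restart. The matter is worth correcting because it changes reported values for a stated secondary objective.

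**What to change.** In Part B Section 8, derive and label steady-state parameters and CL/F, and allow the 0-h/24-h substitution, only for profiles taken on or after the fourth consecutive daily dose at the current dose level, counted from the dosing record. Summarise earlier profiles separately by sampling day, without the steady-state label and without the substitution. The fourth dose matches the start of Part C's 20-mg window. It is adequate for half-lives up to about 12 h, and the sponsor should confirm it against the drug's known half-life.

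In Part C Section 8, apply the same count from the first dose of the current dose level in place of the calendar day.

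The cost is a change of SAP wording and one derived flag from existing dosing dates. No new samples are needed and treatment is untouched. The drawback is that some early Part B profiles leave the steady-state table, which makes a small PK population smaller.

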2.4 Study Treatment

Subjects in the Adult Cohort were scheduled to be treated with 5 mg palovarotene daily for up to 24 months (non-flare-up based treatment); however, some adult subjects chose not to receive non-flare-up based treatment.

Flare-up based treatment will begin as soon as possible after a subject reports onset of a flare-up and the flare-up has been confirmed by the Investigator. In the event of an eligible flare-up, subjects in the Adult Cohort will receive open-label palovarotene treatment as follows:

- 20 mg for 28 days. The first dose will be taken upon flare-up confirmation by the Investigator.
- 10 mg for 56 days, for a total flare-up treatment duration of 84 days; treatment may be extended if the flare-up is ongoing and continue until the flare-up resolves. Dosing will be extended in 4-week intervals and be based on clinical signs and symptoms as assessed by the Investigator.

Subjects not receiving non-flare-up based dosing will only be treated during eligible flare-ups and will receive weight-adjusted doses of 20 and 10 mg palovarotene as follows:

Weight Range Category	20-mg Equivalent	15-mg Equivalent	10-mg Equivalent	7.5-mg Equivalent*	5-mg Equivalent*
20 to <40 kg	12.5 mg	10 mg	6 mg	4 mg	3 mg
40 to <60 kg	15 mg	12.5 mg	7.5 mg	5 mg	4 mg
≥60 kg	20 mg	15 mg	10 mg	7.5 mg	5 mg

* In the event of dose de-escalation.

If the subject experiences intolerable side effects during flare-up based dosing, the dose may be reduced to the next lower dose; if the subject is already receiving the lowest possible dose, then study drug will be discontinued. Treatment may be extended after the 84-day treatment period (flare-up based dosing) if the flare-up is ongoing and continue until the flare-up resolves. Dosing will be extended in 4-week intervals based on clinical signs and symptoms as assessed by the Investigator, with remote visits performed every 2 weeks while on treatment. In the event the subject requires dose de-escalation due to an intolerable side effect for a previous flare-up, then the dose the subject will receive for a subsequent flare-up will be determined by the Investigator and the Medical Monitor.

After the Flare-up Day 84/EOT visit has been conducted and the flare-up is considered resolved, subjects in the Adult Cohort will resume the non-flare-up based treatment.

Subjects not receiving non-flare-up based dosing who do not experience an eligible flare-up will not be treated.

